# 9.2 Reporting Procedures

In all study sites, new confirmed STI infection, including HIV, is reportable to local health departments. We will complete mandatory notification of positive STI results as required by law. Participants will be informed in the informed consent process and counseled when receiving positive STI results that results will be reported to the local or state health department as required by law, and that the health department might contact them to offer treatment or to assess possible onward exposures. Abuse that comes to the attention of study staff will be required to be reported in all three jurisdictions if the abuse is perpetrated on a child (who would be ineligible to participate per the study age criteria), or if the abused person is a vulnerable adult (e.g., elderly person, person in a long-term care facility). We do not anticipate having participants who would be considered to be vulnerable, but if we become aware of abuse to a person meeting this criterion, we will report to state/district authorities as required by law.

### 9.2.1 Serious Adverse Event Reporting

All SAEs require expedited reporting by the Principal Investigator to the Emory IRB. An expedited report of an SAE can be submitted by telephone, fax, or email and must be reported to the IRB and the NIDA project officer within 24 hours of the event being reported to the Investigator.

The expedited report will be followed by a detailed, written SAE report of the event and its resolution as soon as possible but no longer than 72 hours after the study team learns of the event. Follow up information may be required and asked for by the IRB directly, or through the NIDA or its representative. A standardized SAE reporting form will be used.

#### **10 STUDY OVERSIGHT**

A DSMB is not planned for this study. Based on criteria included in the NIDA online guidance on safety monitoring (https://www.drugabuse.gov/funding/clinical-research/guidelines-developing-data-safety-monitoring-plan), monitoring will be done by the Principal Investigator and the Institutional Review Board. This level of monitoring is based on NIDA's criteria that the study is a multicenter clinical trial, but does not propose blinded or high-risk interventions. The intervention and the only medication involved is open label and is FDA approved for the indication to which we are referring men. The study does not provide medication, but rather refers men to clinical providers. Further, the centralized nature of the study data at Emory will facilitate routine monitoring.

#### 11 CLINICAL SITE MONITORING

The principal investigator will monitor data collection throughout the study, and will ensure that interview protocols are followed, all adverse event reports are reviewed (if any), confidentiality procedures are implemented, and the Emory University IRB is alerted if unexpected concerns arise.

#### 12 STATISTICAL CONSIDERATIONS

# 12.1 Study Hypotheses

- 1) The rate of PrEP uptake will be higher among men provided with the HealthMindr app compared to men provided with standard of care.
- 2) Access to additional HIV prevention services available in the HealthMindr app will result in reductions in risk behaviors or greater access to HIV testing services, which are associated with PrEP uptake.
- 3) Individual, social, and community characteristics of participants will be associated with PrEP uptake among participants provided access to the HealthMindr app.

#### 12.2 Sample Size Considerations

Power calculations were conducted for the main analysis of time to PrEP initiation comparing the intervention arm with the control condition. Current estimates of PrEP uptake in the most recent 4 quarters for which data are available are that 4,507 men started PrEP $^{50}$ . Assuming all of these men are MSM, which is an overestimate, and using as the denominator the number of MSM estimated by CDC to be eligible for PrEP22, only 4,507/492,000 = 0.9% of eligible MSM started PrEP between mid-2104 and mid-2015. Thus, our assumption that at most 2% of men in the control arm will initiate PrEP during the study period is conservative. Based on our preliminary pilot data, men using the app initiated at 9% per 4 month period; we conservatively estimate that men in the intervention period would initiate PrEP at 9% in a year. We propose a total sample size of 438 intervention arm and 219 control which will provide 91% power ( $\alpha = 0.05$ ) to detect a 4.5 fold increase in the hazard of uptake in the intervention arm compared to the control arm. If our effect were less than our conservative estimates, we would retain reasonable power (4-fold: 80% power; 3.5-fold: 74% power). These power calculations assume 20% annual attrition.

#### 12.2.1 Efficacy Review

The primary efficacy analysis will be an intent-to-treat analysis. Participants will be analyzed based on the study arm they were assigned to regardless of the level of engagement with the HealthMindr app among intervention arm participants. Because randomization to the intervention arm will not guarantee engagement with the HealthMindr app, we will use two types of secondary analysis to estimate the potential effects of the app under conditions of optimal adherence. First, a per-protocol analysis will estimate the effect of the app on rates of PrEP initiation under assumptions of substantial adherence using principal stratification methods to estimate the causal effects given associations between measured confounders and adherence profiles. Study subjects who participate in the baseline assessment and at least 3 subsequent monthly PrEP screeners during the year will be categorized as substantially adherent for this purpose. Second, level of engagement with the app, including number of times the app is opened per month or number of app features accessed per use, may vary strongly across participants. Under the hypothesis that greater engagement with the app will lead to faster initiation into PrEP, we will model the dose-response relationship between a continuous gradient of app engagement and rate of PrEP initiation among app users in the study.

#### 12.3 Final Analysis Plan

The main analysis will use four standard survival analysis techniques to compare the rate of PrEP initiation by study arm and estimate the size and statistical significance for observed differences. This approach will account for loss-to-follow-up, study termination due to competing events (e.g., HIV seroconversion), and other forms of censoring. The first analysis will use Kaplan-Meier methods to characterize the empirical survival distribution, which here is the timedependent probability of remaining PrEP uninitiated over follow-up. This method will yield estimates of the median time to PrEP initiation and cumulative incidence with 95% confidence intervals. Second, log-rank or related (e.g., Harrington-Fleming) statistical tests will be used to test the null hypothesis of no difference in rates of PrEP initiation by study arm, with a cutoff p value of 0.05 used to determine significance. 52 Third, a Cox proportional hazards model will be used to estimate the hazard ratio associated with study arm to characterize the strength of causal effect of use of the app. The primary model will only include an independent exposure variable for the study arm as randomized (i.e., standard intent-to-treat analysis), but secondary models may include covariates (including those related to the four domains along the PrEP continuum) for which there is descriptive evidence of residual imbalance after randomization. Fourth, parametric survival models (e.g., under exponential or Weibull distributional assumptions) will be used to characterize the rate of PrEP initiation overall and by study arm.

Mediation Analysis: This analysis will examine how study arm assignment may lead to intermediate effects, such as greater access to HIV testing or decreased risk behavior, which themselves are associated with the primary effect of PrEP initiation. Using the difference method for a set of Cox proportional hazards models similar to those in the Aim 2 analyses, log coefficients for the indirect effects will be subtracted from log coefficients for the direct effect to estimate the size of the mediation. Mediators will be selected on the variables known to be associated with the 4 domains of the PrEP continuum (including awareness, access, and engagement with HIV prevention services), and changes in risk behaviors resulting from app utilization.

Moderation Analysis: This analysis will examine how attitudes and beliefs about PrEP, as well as individual, social, and community characteristics can moderate the effect of the app on PrEP initiation. Examples of moderators include perceived benefits of PrEP use, self-assessed

vulnerability to HIV, perceived advantages to meeting partners if currently taking PrEP, and social support for PrEP use within one's social network. Demographic factors such as age, race/ethnicity, and geographic setting will also be critical moderators. Although the distribution of these factors will be balanced across study arm with randomization, they may have effects on the level of engagement in the app (i.e., post-randomization treatment adherence) that itself will influence the rate of PrEP initiation. Given this causal model, we will use instrumental variable analyses to estimate the effect of optimal app use on PrEP initiation given measured and unmeasured moderators.

In-Depth Interview Data Analysis: All IDIs will be digitally recorded, transcribed verbatim, and de-identified. Transcripts will be entered into MAXQDA, which facilitates the processes of coding, annotating, and retrieving text such that analysts may note patterns in the textual data across themes. Data analyses will be conducted using a phenomenological inquiry framework. Phenomenology is focused on describing what a given group of people have in common as they experience a phenomenon, and is an inductive analytic approach that allows the patterns, themes, and categories of analysis to emerge from data. Data are then presented through textual phenomena descriptions based on summaries of experiences described by respondents. Composite descriptions offer explanation of underlying structures which exist across the respondents' experiences.

Our data analysis team will consist of lead analysts and trained analysts at Emory. Analysts will have had previous experience with thematic coding and will attend training on coding guidelines to ensure consistency. After close readings of the text, the lead analysts will create a preliminary codebook to capture emergent themes. We anticipate developing a codebook consisting of 12-15 codes representing key project themes, including explicit domains from the interview guides and from the theoretical basis of our app (deductive themes) and pervasive, unanticipated themes that were emergent across various transcripts (inductive themes). Provisional definitions will be given to each code. The preliminary codebook will be presented to other analysts (per the phenomenological approach) and a group discussion will occur. After edits are made to the codebook, all analysts will apply the preliminary codebook to a single transcript. The coded transcripts will be merged for comparison and code definitions will be revised based on an examination of coding disagreement. This process will be repeated until consistent agreement is attained among all coders. A finalized codebook will be created and the trained analysts will start coding (from scratch) all of the textual data for the project. Coders will also develop brief summaries to describe individual participants in order to help contextualize the thematic analysis across individuals. MAXQDA's search and retrieve functions will then be used to review coded data and identify patterns, including similarities and differences across study sites.

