#### 5.1.1 Inclusion Criteria

- Cis-gender male
- 18-34 years of age (inclusive)
- Resides in one of the study MSAs
- Intends to remain in study area for duration of the trial
- Owns an Android or iOS smartphone and willing to download study app
- Able to read and understand English without assistance
- Reports having anal sex with a man in the past 6 months
- Reports being HIV negative or never tested for HIV

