# 5.4 Subject Withdrawal

Participants may voluntarily withdraw from the study for any reason at any time. The study investigators also may withdraw participants from the study in order to protect participant or staff safety. Study staff will record the reasons for all withdrawals or holds from the study on a Study Stop Form in the participants' study records.

Participants who seroconvert will be asked to participate in in-depth interviews (IDI). All of the participants will be followed per standard protocol for linkage to care. Participant will then be withdrawn from study activities.

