# 8.2 Laboratory Procedures/Evaluations

**HIV Testing:** Participants in the intervention arm will be offered at-home HIV test kits up to 2 times during their 12 months of participation through the Emory CFAR. HIV is tested using FDA-approved OraQuick test using a mouth swab. Results can be verified through self-report.

**STI Testing:** Participants in the intervention arm will be offered at-home STI test kits up to two times during their 12 months of participation; through the Emory CFAR. Diagnosis of an STI is an indication for PrEP. The presence of C. trachomatis (CT) and N. gonorrhea (NG) in self-collected urethral, throat, and rectal specimens will be determined by using the Aptima Combo 2 CT/NG assay or Abbott Real Time CT/NG assay, an FDA-cleared real-time polymerase chain reaction (PCR) assay for direct, qualitative detection of a region of the cryptic plasmid DNA of CT and the Opa gene of NG. Syphilis screening will be conducted using the TREP-SURE EIA assay with reflexive rapid plasma reagin (RPR) test for reactive results; participants with a reactive result will be referred to a local provider for treatment and follow-up. Positive STI test results will be provided to participants over the phone by a study staff member who can refer participants to treatment. Upon request, copies of results may also be sent to the study participant.

**Alcohol and Substance Use Screening:** Residual urine from STI testing will be screened for alcohol and substance use. This will be done as a confirmation of self-report for substance use for research purposes only and results will not be reported back to participants. Participants who wish to receive referrals for assistance with substance use will be assisted with navigation services by study staff.

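### Section 12.3 calls HIV seroconversion a competing event but censors it and reads cumulative incidence from Kaplan-Meier, which slightly overstates the share of men who start PrEP

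*Combined protocol and SAP*

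**What the plan says.** Section 12.3 (Final Analysis Plan) states that the survival approach will deal with loss to follow-up, "study termination due to competing events (e.g., HIV seroconversion"), and other kinds of censoring, all in one list. Of Kaplan-Meier it then says: "This method will yield estimates of the median time to PrEP initiation and cumulative incidence with 95% confidence intervals". For the effect size, "a Cox proportional hazards model will be used to estimate the hazard ratio associated with study arm", with arm as the only term in the primary model. No competing-risk estimator and no sensitivity analysis for HIV is listed.

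Four other places bear on the point.
- Section 5.4: "Participants who seroconvert will be asked to participate in in-depth interviews (IDI"), are linked to care, and then "Participant will then be withdrawn from study activities".
- Section 8.2: "Participants in the intervention arm will be offered at-home HIV test kits up to 2 times during their 12 months of participation". Kit results can be verified by self-report. No such offer is described for controls.
- Section 5.1.1 admits a man who "Reports being HIV negative or never tested for HIV", so undiagnosed infection at entry is possible.
- Section 12.1, hypothesis 2, and the mediation paragraph of section 12.3 expect the app to raise access to HIV testing.

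**The concern.** A man with HIV is no longer a candidate for PrEP; section 2.1 itself describes PrEP as depending on serostatus. Kaplan-Meier censoring assumes that a man who leaves would have gone on to start PrEP at the same rate as those who remain. For seroconverters that rate is zero. The complement of the Kaplan-Meier curve therefore estimates uptake in a setting where nobody acquires HIV, not the share of randomised men who start. The plan says the competing event is accounted for, and with this estimator it is not.

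The second issue is the comparison between arms. HIV-positive men are non-starters. Once detected they leave the risk set; undetected they stay in it and dilute the observed rate. If the app arm detects more of them, its denominator shrinks more than the control denominator, and the hazard ratio moves up a little. At stake are the accuracy of the reported uptake percentages and, to a lesser degree, the hazard ratio. The significance test is not seriously affected.

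**Working it through.** **Inputs from section 12.2.** 438 app and 219 control men; 9% and 2% initiating in 12 months; 20% attrition; alpha 0.05 (two-sided assumed).

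**The plan's own figure.** Two-proportion test with 438 × 0.8 = 350.4 and 219 × 0.8 = 175.2 men: pooled proportion 0.0667, null SE 0.02308, alternative SE 0.01859. Power = Φ[(0.07 − 1.96 × 0.02308)/0.01859] = 90.9%, against 91% stated. The starting rates can be used as given.

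**Hazards.** App: −ln(0.91) = 0.0943 a year. Control: −ln(0.98) = 0.0202. Their ratio is 4.67.

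**Assumed, not in the documents.** HIV incidence, undiagnosed HIV at entry, and the rate at which each arm detects it. Ranges are shown.

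**Step 1: Kaplan-Meier against the true share, app arm.** With PrEP hazard l = 0.0943 and HIV detected and censored at hazard c, one minus Kaplan-Meier is 1 − exp(−l) = 9.00% whatever c is. The true share is the Aalen-Johansen quantity l/(l + c) × [1 − exp(−(l + c))].

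| HIV per year | 1 − KM | True share | Gap (points) |
|---|---|---|---|
| 1% | 9.00% | 8.96% | 0.04 |
| 3% | 9.00% | 8.87% | 0.13 |
| 5% | 9.00% | 8.78% | 0.22 |

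For example, at 5%: 0.0943/0.1443 × (1 − exp(−0.1443)) = 8.78%. The gap arises only when HIV is detected. An arm that detects none keeps positive men as non-starters, and its Kaplan-Meier estimate then equals the true share.

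**Step 2: hazard ratio.** Positive men have zero PrEP hazard and leave the risk set only when detected. The ratio of events per person-time stands in for the Cox hazard ratio. In the most unequal case (immediate detection in the app arm, none in control) and with no HIV at entry, the inflation factor is about c/(1 − exp(−c)).

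| HIV at entry | HIV per year | Immediate app, no control detection | Partial: app 2/yr, control 0.5/yr | Equal: 1/yr in both |
|---|---|---|---|---|
| 0% | 1% | 1.005 | 1.001 | 1.000 |
| 0% | 3% | 1.015 | 1.004 | 1.000 |
| 0% | 5% | 1.025 | 1.007 | 1.000 |
| 5% | 3% | 1.069 | 1.022 | 0.999 |
| 10% | 5% | 1.140 | 1.043 | 0.997 |

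Under immediate detection in the last two rows, the app arm's Kaplan-Meier estimate stays at 9.00% while the true shares are 8.43% and 7.90%.

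**Step 3: scale.** Expected events are 350.4 × 0.09 = 31.5 and 175.2 × 0.02 = 3.5, about 35 in all. The SE of the log hazard ratio is 1/√(35.04 × 2/9) = 0.36 by Schoenfeld, or √(1/31.5 + 1/3.5) = 0.56 from the events by arm. A 5% shift is ln(1.05) = 0.049, or 0.09 to 0.14 SE. The extreme 14% is ln(1.14) = 0.131, or 0.23 to 0.37 SE. A 5% shift under the null moves the type I error from 0.050 to between 0.051 and 0.052.

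**The case against.** The strongest reply is that censoring seroconverters in a Cox model is not a mistake: it gives the cause-specific hazard ratio, a standard estimand. That stands, and it is why the primary test and model need not change. It does not rescue the cumulative incidence, for which one minus Kaplan-Meier is the wrong estimator.

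A reader might infer from the app-only kits that the hazard ratio is overstated and that the bias always favours the app. The documents do not support that. Inflation needs a difference in detection, and what is documented is a difference in offers. Section 6.1.1 has follow-up surveys asking HIV testing history and status, and section 4 makes the quarterly surveys the same in both arms apart from final acceptability items. Controls are referred to outside resources that include HIV testing locators (section 7.2, Appendix C). Kits are optional and their results rely on self-report. Section 2.1 puts past-year HIV testing among MSM at 58% to 71% in two surveys, so detection among controls need not be low. On the other side, unequal detection is plausible: it is close to what hypothesis 2 predicts, and the app encourages a plan to test 2 to 4 times a year (section 6.1). The direction is possible, not established.

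The larger factors in step 2 depend on infection already present at entry. Section 5.4 speaks only of men who seroconvert, and no section says how a man positive at entry and found later is handled. Those figures show why the two groups should be reported separately; they do not predict the bias in this trial.

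Finally, keeping men withdrawn for HIV in the risk set to month 12 changes the estimand to a subdistribution-type hazard ratio. It also exempts detected men from attrition that undetected men still face, a small asymmetry in the other direction. Reasonable statisticians differ on making this primary, so it belongs in a sensitivity analysis.

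**Conclusion.** The estimator point holds on the text alone and needs no difference between arms: a named competing event is censored, and Kaplan-Meier is used for cumulative incidence. The overstatement is about 0.04 to 0.22 points on 9% if HIV is detected and censored at 1% to 5% a year. Those rates are assumptions.

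The between-arm point holds only conditionally. If HIV is detected more often in the app arm, its cumulative incidence is overstated more and the hazard ratio is slightly inflated: 0.1% to 4.3% under the partial-detection range, and 0.5% to 2.5% at the upper bound for new infections alone. If detection is equal, the hazard ratio is essentially unchanged (0.997 to 1.000). The model assumes constant hazards and uses a person-time ratio in place of the Cox estimate. Any likely shift is small beside sampling error and does not threaten the primary test. This is a minor correction worth making because it is cheap.

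**What to change.** In section 12.3:
1. Estimate cumulative incidence of PrEP initiation by arm with the Aalen-Johansen estimator, HIV as a competing event, in place of one minus Kaplan-Meier.
2. Keep the log-rank test and the Cox model as primary, and say that the hazard ratio is cause-specific.
3. Add a sensitivity analysis that keeps men withdrawn for HIV in the risk set as non-initiators to month 12 in both arms.
4. Report HIV withdrawals by arm, separating infection present at entry from new infection where known.

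The cost is SAP wording, a little more analysis in standard software, and a slightly lower reported cumulative incidence. No new data are needed, and the withdrawal rule in section 5.4 stays as it is.
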